7.2 Number of subjects needed

This trial will be conducted at approximately 25 sites in Europe and North America. The anticipated minimum number of randomised subjects per trial site is 6 and the maximum number of subjects per trial site is 30.

Assuming a screening failure rate of 35%, approximately 385 subjects will be screened and approximately 250 subjects will be randomly assigned to a treatment group in the trial (50 subjects in each of the 5 treatment groups: delgocitinib cream 1, 3, 8, and 20 mg/g and delgocitinib cream vehicle). The statistical power considerations for this sample size are described in Section 14.1.

The randomisation is stratified by the severity of chronic hand eczema according to IGA (IGA score of 2 [mild], 3 [moderate], or 4 [severe]) and region (Europe and North America).

A lower limit of 20% and an upper limit of 30% will be imposed on the IGA baseline severity of subjects with mild and severe chronic hand eczema, respectively. Based on this capping, the overall number of subjects in each severity group can range between:

- Mild: 50 to 75 subjects.
- Moderate: 100 to 150 subjects.
- Severe: 50 to 75 subjects.

A maximum of 50 subjects will be randomised in the North American region.

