Patients with hand eczema represent a heterogeneous patient population as hand eczema is associated with different aetiologies and morphologies and the severity may range from mild to severe. To mitigate any potential difference in trial outcome based on baseline characteristics, the trial subjects will be randomised in stratified manner as described in Section 9.3. The randomisation will minimise selection bias and minimise influence of (intrinsic) confounding factors and the stratification will ensure a certain balance of the treatment groups with respect to disease severity and region. The enrolment is controlled by disease severity to allow for assessment of co-variability in patients with mild, moderate, and severe disease state.

The inclusion of 4 active treatment groups with 1, 3, 8, and 20 mg/g of delgocitinib cream and a vehicle control group is considered enough to establish a dose-response signal. The vehicle control group will serve as reference and has been added to establish the efficacy and safety of delgocitinib cream in a blinded trial design.

The trial endpoints have been selected to evaluate the efficacy of delgocitinib in improving the severity and extent of chronic hand eczema. Both IGA and HECSI will be used in this clinical trial as investigator-rated assessments of disease severity. The IGA is an assessment of the overall disease severity at a given time point and is based on a 5-point scale describing the severity of the disease from “clear” to “severe”. The HECSI is an instrument used to score both the extent and the intensity of the disease. The primary endpoint of the trial is to evaluate the percentage of subjects achieving treatment success defined as an IGA score of 0 (clear) or 1 (almost clear) with at least a 2-step improvement from baseline to Week 16. The trial endpoints will also address subject’s perception of disease severity and the impact on sleep, daily activity, and health-related quality of life.

13 Adverse events

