14.1 Sample size

A total of 250 subjects will be divided into 5 treatment groups and randomised 1:1:1:1:1 to one of each dose level of delgocitinib cream (1, 3, 8, or 20 mg/g) or delgocitinib cream vehicle.

The sample size is based on the following pairwise consideration, even though the primary objective of the trial is to establish the dose-response relationship. With a significance level of 5% when comparing 2 treatment groups and assuming treatment success rates (according to IGA) of 45% and 15%, respectively of the investigative treatment group (delgocitinib cream) and delgocitinib cream vehicle, then 50 subjects per treatment group will provide a power slightly above 90% for finding significantly different success rates between treatment groups.

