14.3.5 Analysis of primary efficacy endpoint

The primary endpoint IGA TS at Week 16 will be analysed for the full analysis set and for the per protocol analysis set. The per protocol analysis is regarded as supportive.

IGA TS refers to IGA score of 0 (clear) or 1 (almost clear) with ≥ 2 -step improvement from baseline.

For the analysis of the primary endpoint, subjects who initiate rescue medication before Week 16 or withdraw from the trial and have no retrieved data at Week 16, will all be considered non-responders.

The Multiple Comparison Procedure – Modelling (MCP-Mod) approach (see e.g., EMA Qualification Opinion of MCP-Mod [23] or Bretz et al [24] for further details of the framework) will be used to guide dose selection. The dose-response relationship for the binary endpoint IGA TS will be modelled by the following 3 identified candidate models. These candidate models are selected based on the expected dose-response.

Linear in log: $E_0 + \delta \times \log(d + c)$,

E_{max} : $E_0 + E_{max} \times d / (ED_{50} + d)$,

Sigmoid E_{max} : $E_0 + E_{max} \times d^h / (ED_{50}^h + d^h)$,

where d is the dose (incl. vehicle), E_0 is the efficacy offset (anticipated vehicle effect), E_{max} is the asymptotic maximum effect, ED_{50} is the half-life value of E_{max} , h is the steepness at ED_{50} , δ is the slope parameter, and c is a fixed offset parameter.

The models will be adjusted for the stratification variables region and baseline IGA. The model parameters (ED_{50} , h) will be prespecified a priori by suitable guesses based on data from Japan Tobacco's dose-ranging trial QBA2-1 (25). Akaike's Information Criteria will be

used as the goodness-of-fit criterion that will drive the selection of the dose-response model that fits data best while controlling the family-wise error rate at 5%. Based on the selected model, the dose-response relationship will be estimated and presented with 2-sided 95% CI. If none of the candidate models converge, other possibilities of models and goodness-of-fit criteria will be explored. The dose-response modelling will be performed on both the total population and subjects having a baseline IGA of 3 or 4, in order to further explore heterogeneity in the disease population.

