14.3.12 General principles

Unless otherwise stated, all significance tests will be 2-sided using the 5% significance level. All CIs will be presented with 95% degree of confidence.

An observed-cases approach will be used for tabulations of data by visit (i.e., involving only those subjects who attended each specific visit).

Categorical data will be summarised using the number and percentage of subjects in each category and treatment group. Continuous data will be summarised using the mean, median, standard deviation, minimum, and maximum values.

All the analyses specified in the protocol will be reviewed in relation to the blinded data actually obtained and the statistical analysis plan will be finalised before breaking the randomisation code.

Any changes from the statistical analysis planned in this clinical trial protocol will be described and justified in a protocol amendment, the statistical analysis plan and/or in the CTR dependent on the type of deviation.

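### Fitting the dose-response model to the total population and to the IGA 3–4 subset that forms 70–80% of it shows only about 20–30% of any mild versus IGA 3–4 difference, and no estimate by severity class is planned

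*Combined protocol and SAP*

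**What the plan says.** Section 14.3.5 states how heterogeneity will be explored for the primary endpoint: "The dose-response modelling will be performed on both the total population and subjects having a baseline IGA of 3 or 4". Section 14.3.6 carries the same modelling approach over to the HECSI change.

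Section 7.2 controls the severity mix: "A lower limit of 20% and an upper limit of 30% will be imposed on the IGA baseline severity" for mild and for severe subjects. The resulting counts are given there, for example "Mild: 50 to 75 subjects", with the same range for severe and 100 to 150 for moderate. Section 12 gives the reason: "The enrolment is controlled by disease severity to allow for assessment of co-variability in patients with mild, moderate, and severe disease state".

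Elsewhere in the efficacy analyses, baseline IGA is a covariate (dose-response models, MMRM) or a stratification factor (Cochran-Mantel-Haenszel and log-rank tests). Exploratory efficacy subgroups in Section 14.3.7.3 are by aetiology. Severity is used for baseline tables (14.3.2) and biomarkers (14.3.8).

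**The concern.** The two sets overlap heavily, so their results must look alike even when mild subjects respond quite differently. Two similar curves, each with its own confidence band, invite the conclusion that severity does not matter. The comparison also says nothing about moderate versus severe, because those classes are merged in both fits.

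Heterogeneity is plausible from the endpoint alone. IGA TS needs a score of 0 or 1 and a 2-step improvement, so a subject starting at IGA 2 must reach 0, while one starting at 3 or 4 may succeed at 1. The severity limits can turn away otherwise eligible subjects (Section 9.3), yet no efficacy result is reported for any single class. Section 5.3 says the results will support phase 3, so an unreported pattern by severity would be a practical loss.

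**Working it through.** **Inputs.** 250 subjects, five arms, 50 per arm (14.1). Tests are two-sided at 5% (14.3.12). Planning success rates are 45% active and 15% vehicle (14.1). Mild subjects number 50 to 75 (7.2). Randomisation is stratified by IGA (7.2), so the mild share is about equal across arms.

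**1. The plan's own figure.** Section 14.1 says that "50 subjects per treatment group will provide a power slightly above 90" per cent. With the pooled chi-square form, the mean rate is 0.30:
- critical difference = 1.96 × √(2 × 0.30 × 0.70 / 50) = 0.180
- SE under the alternative = √((0.45×0.55 + 0.15×0.85)/50) = √(0.375/50) = 0.0866
- power = Φ((0.30 − 0.180)/0.0866) = Φ(1.39) = 91.8%

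The figure is reproduced.

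**2. Mild share.** m = 50/250 = 0.20 to 75/250 = 0.30. IGA 3–4 is therefore 80% to 70% of the total (175 to 200 subjects). Per arm: 10–15 mild and 35–40 IGA 3–4.

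**3. Dilution on the rate-difference scale.** With balanced shares,

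total effect = m × (mild effect) + (1 − m) × (IGA 3–4 effect),

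so total − IGA 3–4 = m × (mild − IGA 3–4). Taking the planning effect of 30 points in IGA 3–4 and assumed values in mild subjects:

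| m | Mild effect | Total effect | Visible gap | True gap |
|---|---|---|---|---|
| 0.20 | 0 | 24 | 6 | 30 |
| 0.30 | 0 | 21 | 9 | 30 |
| 0.20 | 15 | 27 | 3 | 15 |
| 0.30 | 15 | 25.5 | 4.5 | 15 |

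**4. Logit scale, adjusted for baseline IGA.** Expected data were fitted with 45% versus 15% in IGA 3–4. The log odds ratio there is 1.534. With 15% in both mild groups and m = 0.20 the total fit gives 1.313, and the visible fraction is (1.313 − 1.534)/(0 − 1.534) = 0.14.

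| Mild rates (active, vehicle) | m = 0.20 | m = 0.30 |
|---|---|---|
| 30%, 15% | 0.18 | 0.27 |
| 15%, 15% | 0.14 | 0.22 |
| 10%, 10% | 0.10 | 0.17 |

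**5. What the overlap does to precision.** One dose versus vehicle, using the planning variance 0.375 in both classes:
- SE of the direct mild versus IGA 3–4 contrast: √(0.375/10 + 0.375/40) = 21.7 points, or √(0.375/15 + 0.375/35) = 18.9 points.
- SE of the nested contrast with the overlap allowed for is m times this: 4.3 or 5.7 points. The ratio to its SE is unchanged (30/21.7 = 6/4.3 ≈ 1.39; 30/18.9 = 9/5.7 ≈ 1.59).
- Treating the two fits as independent gives SEs of 13.0 and 13.5 points, against visible gaps of 6 and 9. The ratios fall to 0.46 and 0.67.

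**6. What direct estimates could deliver.** Power for a 30-point interaction is Φ(1.39 − 1.96) = 28% to Φ(1.59 − 1.96) = 35% per dose. Pooling the four active arms gives SEs of 15.4 and 13.4 points and power of about 50% to 61%. For the effect in mild subjects alone, assuming 20% versus 10% success, 95% half-widths are:
- per dose: 1.96 × √(0.25/10) = 31 points, or 1.96 × √(0.25/15) = 25 points
- active arms pooled: 1.96 × √(0.16/40 + 0.09/10) = 22 points, or 1.96 × √(0.16/60 + 0.09/15) = 18 points

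**The case against.** - *No formal contrast is named.* Section 14.3.5 specifies two fits and a purpose, with no subtraction, test or decision rule. This stands. The IGA 3–4 curve is also a valid result by itself. Reading the fits side by side is still the only use that serves the stated purpose.
- *No information is lost.* Step 5 confirms this for a contrast that allows for the overlap, and the mild effect could be back-calculated on the rate-difference scale. The weakness lies in the display and in the absence of any such contrast or direct estimate.
- *Section 12 promises no class-specific effects.* A reader might infer that the severity limits exist to estimate efficacy in each class. The wording about co-variability is ambiguous and can mean covariate adjustment, which is planned. It does not support that reading.
- *The SAP may add this.* Section 14.3.12 foresees a SAP finalised before unblinding, and no separate SAP text appears in the combined document. However, Sections 14.3.5 and 14.3.6 defer only sensitivity analyses to it.
- *Class estimates are weak and many.* Three classes, four doses and two endpoints give 24 estimates without multiplicity control. At 10 per arm, 20% versus 10% means about 2 versus 1 expected responders. This stands, and it limits what the change can achieve.

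**Conclusion.** The point holds as a weakness in an exploratory analysis. The visible difference between the two fits is 0.20–0.30 of the true mild versus IGA 3–4 difference. That factor is exact only for rate differences with the mild share balanced across arms. On an IGA-adjusted logit scale the dilution was similar or stronger (0.10–0.27), under assumed rates; Section 14.3.5 does not state the model scale. No efficacy estimate by baseline IGA class and no dose-by-severity term is planned, and moderate and severe are never separated.

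A reader might go further and conclude that the trial as planned cannot show whether the cream works in mild disease. The documents do not support blaming the analysis for that. With 10–15 mild subjects per arm it is largely a sample-size limit, which a better analysis would not remove. The primary analysis and its error control are unaffected.

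**What to change.** Keep the IGA 3–4 curve. Add to Sections 14.3.5 and 14.3.6, labelled exploratory:

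- (a) The difference versus vehicle in IGA TS and in HECSI change, with 95% CI, in each non-overlapping baseline IGA class (2, 3 and 4), per dose and with the active arms pooled. Use small-sample intervals (score or exact) for IGA TS.
- (b) One dose-trend by baseline-IGA interaction term, fitted on the full analysis set.

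State that the total and IGA 3–4 fits overlap and that their similarity is not evidence of a common effect.

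The cost is SAP wording and reruns of existing code by a factor already used for stratification, with no new data, subjects or alpha. The additions can be prespecified before the randomisation code is broken. The price is a larger set of imprecise, unadjusted estimates that must be read as descriptive.

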14.3.6 Analysis of secondary efficacy endpoints

The secondary endpoints change from baseline to Week 16 in HECSI and time to IGA TS will be analysed for the full analysis set and for the per protocol analysis set. The per protocol analysis is regarded as supportive.

For the analysis of the change from baseline to Week 16 in HECSI, data collected after permanent discontinuation of IMP or after initiation of rescue medication will not be included in the analysis. Missing data at Week 16 will be imputed using the mixed model for repeated measurements (MMRM) predicted values from the below specified model for repeated measurements.

The dose-response modelling approach suggested for the primary endpoint will also be applied for the continuous endpoint change from baseline to Week 16 in HECSI.

In addition to the dose-response modelling approach, the continuous endpoint will be analysed using a MMRM on the post baseline responses up to Week 16 with an unstructured

covariance matrix, Kenward-Roger approximation to estimate denominator degrees of freedom, and the mean modelled as follows:

Change from baseline in HECSI

$$= \text{treatment} \times \text{visit} + \text{baseline HECSI} \times \text{visit} + \text{region} + \text{baseline IGA}$$

The estimates will be presented with nominal p-values and 95% CI at each visit. The primary comparison between each delgocitinib dose and vehicle will be at Week 16.

Time to IGA TS response is defined as the time from baseline to first assessment of an IGA TS. Subjects will be censored at the date of the last assessment visit or at initiation of rescue medication, whichever occurs first. Kaplan-Meier curves of time to IGA TS will be estimated and presented by treatment for the full analysis set. Treatment groups will be compared using a 2-sided log-rank test stratified by region and baseline IGA.

Sensitivity analysis will be performed as applicable in order to assess the robustness of results of the primary analysis with respect to the retrieved data at Week 16 and assumptions regarding missing data. This will be described in further detail in the statistical analysis plan.

14.3.7 Analysis of other endpoints

14.3.7.1 Analysis of patient-reported outcomes

The PROs HEIS, PaGA, DLQI, EQ-5D-5L, QOLHEQ, WLQ, and PGI-C will be summarised by treatment group and visit using descriptive statistics. The summaries will be presented for the full analysis set.

The HESD collected in the eDiaries on a daily basis (all individual symptoms) will be summarised over time by treatment group using descriptive statistics. The summaries will be presented for the full analysis set.

The daily diary recordings of the HESD NRS scores will be derived into discrete weekly endpoints based on calendar time (with the exception of Week 16) from baseline visit i.e., the endpoints represent the nominal week and are not directly related to the actual visit in contrast to other visit based assessments. The algorithm for deriving the endpoints at each time point is described as follows: baseline weekly average will be defined by average of measurements from Day -7 to Day -1, Week 1 weekly average will be defined by the average of measurements from Day 1 to Day 7, Week 2 weekly average will be defined by the average of measurements from Day 8 to Day 14 and so on, until Week 15. Week 16 will be calculated

based on the 7 days preceding the Week 16 visit. A minimum of 4 HESD NRS scores out of the 7 days are required to calculate the average score. This will be derived for each symptom, respectively.

In the subgroup of subjects with a baseline worst pruritus (weekly average) – one of the symptoms captured in the HESD – score of at least 4, the proportion of subjects with reduction in worst pruritus (weekly average) of at least 4 from baseline to Week 16 will be summarised by treatment group and analysed using the Cochran-Mantel-Haenszel approach as described for the analysis of the primary endpoint.

PaGA TS refers to achieving:

- PaGA score of 0 (clear) when classified at baseline as 1 (almost clear) or 2 (mild)
or
- PaGA score of 0 (clear) or 1 (almost clear) when classified at baseline as 3 (moderate) or 4 (severe).

The proportion of subjects achieving PaGA TS at Week 16 will be summarised by treatment group and analysed using the Cochran-Mantel-Haenszel approach as described for the analysis of the primary endpoint.

The time to PaGA TS will be summarised by treatment group and analysed as described for the primary analysis of the secondary time to event endpoint.

In the subgroup of subjects with a baseline DLQI score of at least 4, the proportion of subjects with a reduction in DLQI score of at least 4 at Week 16 will be summarised by treatment group and analysed using the Cochran-Mantel-Haenszel approach as described for the analysis of the primary endpoint.

The change from baseline to Week 16 in HESD NRS (weekly average for each individual symptom), HEIS (for each individual item), DLQI, EQ-5D-5L, QOLHEQ, and WLQ will be summarised by treatment group and domain, where applicable, and analysed using the MMRM approach as described above for the analysis of the secondary continuous endpoint.

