Primary objective	
Primary and secondary endpoints
 
Primary endpoint
 
 Investigator's Global Assessment (IGA) score of 0 (clear) or 1 (almost clear) with at least a 2-step improvement (IGA TS) from baseline to Week 16. 
Secondary endpoints
 
 Change in Hand Eczema Severity Index (HECSI) from baseline to Week 16. Time to IGA TS.
Other objectives	
Other endpoints
 
Safety and tolerability
 
 Number of adverse events (AEs). 
Health-related quality of life and efficacy
 
 Change in Chronic Hand Eczema Symptom Diary (HESD) (weekly average for each individual symptom) from baseline to Week 16. 
 Reduction in worst pruritus ("itch" – one of the symptoms captured in HESD) (weekly average) of ≥ 4 points from baseline to Week 16 among subjects with baseline worst pruritus (weekly average) ≥ 4. Change in Chronic Hand Eczema Impact Scale (HEIS) from baseline to Week 16. Patient's Global Assessment (PaGA) TS at Week 16. PaGA TS refers to achieving: PaGA score of 0 (clear) when classified at baseline as 1 (almost clear) or 2 (mild), or PaGA score of 0 (clear) or 1 (almost clear) when classified at baseline as 3 (moderate) or 4 (severe). Time to PaGA TS.

Objectives	Endpoints

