
To evaluate the effect of delgocitinib on Staphylococcus aureus colonisation of the skin, skin microbiome, skin barrier function, and skin inflammation.
	
 Reduction in Dermatology Life Quality Index (DLQI) of ≥ 4 points from baseline to Week 16 among subjects with baseline DLQI ≥ 4. Change in DLQI score from baseline to Week 16. Change in EuroQoL 5-dimension 5-level questionnaire (EQ-5D-5L) from baseline to Week 16. Change in Quality of Life in Hand Eczema Questionnaire (QOLHEQ) from baseline to Week 16. Change in Work Limitation Questionnaire (WLQ) from baseline to Week 16. 
Efficacy over time
 
 IGA TS at each scheduled assessment until and including Week 14. PaGA TS at each scheduled assessment until and including Week 14. Change from baseline to each week from Week 1 to Week 15 in HESD (weekly average for each individual symptom). 
 Reduction of worst pruritus (weekly average) of ≥ 4 points from baseline to each week from Week 1 to Week 15 among subjects with baseline worst pruritus (weekly average) ≥ 4. Change from baseline to each scheduled assessment until Week 14 in HEIS. Change in DLQI score from baseline to each scheduled assessment until Week 14. Reduction of DLQI of at least 4 points from baseline to each scheduled assessment until Week 14. 
Biomarkers
 
 Change in Staphylococcus aureus colonisation from baseline to Week 16. Change in microbiome composition from baseline to Week 16. Change in skin barrier function, measured as transepidermal water loss, capacitance, skin pH, and content of natural moisturising factors, from baseline to Week 16. Change in expression of skin barrier proteins and in extent of immune cells in skin biopsies from baseline to Week 16.

7 Trial design

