11.7.1.2 Chronic Hand Eczema Impact Scale (HEIS)

The HEIS includes 9 items addressing the subject’s perception of the impact of hand eczema on their daily activities, emotional wellbeing, sleep, and work over the past 7 days. Each item is scored on a 5-point scale (0=‘not at all’, 1=‘a little’, 2=‘moderately’, 3=‘a lot’, 4=‘extremely’). The total score is the sum of the 9 items. The highest possible score is 36 and a high score is indicative of a high impact. Domain scores can be calculated for daily activities (4 items), emotional wellbeing (3 items), sleep (1 item), and work (1 item). The HEIS will be completed at the trial site according to the schedule of trial procedures in Section 4.

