14.3.7.2 Efficacy over time

To further explore possible early onset of effect and general efficacy over time, the following endpoints will be evaluated at each scheduled assessment up to Week 14 or each week up to Week 15:

- IGA TS at each scheduled assessment until Week 14.
- PaGA TS at each scheduled assessment until Week 14.
- Change from baseline to each week through Week 1 to 15 in HESD NRS (weekly average for each individual symptom).
 - Reduction of worst pruritus (weekly average) – one of the symptoms captured in the HESD – of at least 4 from baseline to each week through Week 1 to 15 among subjects with baseline worst pruritus (weekly average) of at least 4.
- Change from baseline to each scheduled assessment until Week 14 in HEIS (for each individual item).
- Change in DLQI score from baseline to each scheduled assessment until Week 14.
- Reduction of DLQI of at least 4 from baseline to each scheduled assessment until Week 14.

For the binary endpoints, the same Cochran-Mantel-Haenszel test as for the Week 16 assessment will be applied. For the continuous endpoints, the repeated measurements model already described previously for the Week 16 assessments facilitates that the p-values, treatment differences and 95% CIs can be derived for each visit up to Week 14 (or Week 15 for the change in HESD NRS (weekly average)).

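### Change in HEIS is a listed endpoint with a defined total score, but the planned model is specified item by item, so no estimate or test is planned for the total

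*Combined protocol and SAP*

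**What the plan says.** Section 6, Panel 3, places HEIS among the other endpoints. The Week 16 entry is "Change in Chronic Hand Eczema Impact Scale (HEIS) from baseline to Week 16" and the over-time entry is "Change from baseline to each scheduled assessment until Week 14 in HEIS". Neither names items, domains or the total.

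Section 11.7.1.2 gives the scoring: nine items, each 0 to 4. "The total score is the sum of the 9 items", with a maximum of 36. It adds: "Domain scores can be calculated for daily activities (4 items), emotional wellbeing (3 items), sleep (1 item), and work (1 item".

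Section 14.3.7.1 sets the Week 16 analysis. In a list of six questionnaires, HEIS enters as "HEIS (for each individual item". The list "will be summarised by treatment group and domain, where applicable, and analysed using the MMRM approach" used for the continuous secondary endpoint. Section 14.3.7.2 repeats the restriction for earlier visits: "Change from baseline to each scheduled assessment until Week 14 in HEIS (for each individual item".

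Section 14.3.7.1 also provides a descriptive summary: "The PROs HEIS, PaGA, DLQI, EQ-5D-5L, QOLHEQ, WLQ, and PGI-C will be summarised by treatment group and visit using descriptive statistics". It does not say which HEIS score is summarised, and it involves no test.

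**The concern.** The endpoint list and the analysis text do not describe the same quantity. Panel 3 does mark symptom-level endpoints when it means them: its HESD entries say that each symptom is taken separately, and the analysis sections match. HEIS carries an item qualifier only in the analysis sections. In the Section 14.3.7.1 list, DLQI and QOLHEQ also have defined totals (Sections 11.7.1.5 and 11.7.1.7) and are not restricted to items. No reason is given for treating HEIS differently.

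What is at stake is interpretability. One trial objective is to evaluate health-related quality of life against vehicle. On HEIS, a reader of the report would find nine item results per dose at nominal significance, no stated lead among them, and no single treatment difference. The choice of which items to stress would be open after unblinding.

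**Working it through.** **Plan's own figures.** The documents give no standard deviation, effect size, inter-item correlation or power for HEIS. The only power statement (Section 14.1: 50 per group, 45% against 15% success, slightly above 90%) reproduces at 91.8% with a pooled-variance normal approximation. It concerns IGA treatment success and says nothing about HEIS.

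**What is planned for each HEIS score**

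| Score | Defined in 11.7.1.2 | Repeated-measures model in 14.3.7.1 and 14.3.7.2 |
|---|---|---|
| Nine items | Yes, 0 to 4 each | Yes, stated in both |
| Four domains | Yes, optional | Possibly at Week 16, through the general domain clause in 14.3.7.1 |
| Total | Yes, 0 to 36 | Not stated in either |

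**Number of contrasts against vehicle**
- Inputs: 9 items (Section 11.7.1.2); 4 active doses; HEIS at Week 16 and at eight earlier post-baseline visits, Weeks 1, 2, 4, 6, 8, 10, 12 and 14 (Section 4, Panel 2).
- Week 16: 9 × 4 = 36 by item, against 1 × 4 = 4 for a total.
- Earlier visits: 9 × 4 × 8 = 288 by item, against 1 × 4 × 8 = 32 for a total.

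Section 14.3.12 sets a 2-sided 5% level and no multiplicity rule is given for the items. If tests were independent, the chance of at least one false positive would be 1 − 0.95^9 = 37% for one dose and 1 − 0.95^36 = 84% for all 36. Both are upper illustrations, because items are correlated and the doses share one vehicle group.

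**Scale.** An item's change runs from −4 to +4, at most nine integer values. The total's change runs from −36 to +36. The normal-theory model suits the second better.

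**Precision, illustration only.** Assume nine items with equal variance, equal standardised effect d and common correlation r. The summed effect is 9d in item standard deviations, and the variance of the sum is 9(1 + 8r). The total's standardised effect is therefore d × √(9/(1 + 8r)).

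| r (assumed) | 9/(1 + 8r), equivalent sample-size multiple | Effect ratio, total to one item |
|---|---|---|
| 0.3 | 9/3.4 = 2.65 | 1.63 |
| 0.5 | 9/5.0 = 1.80 | 1.34 |
| 0.7 | 9/6.6 = 1.36 | 1.17 |
| 0.9 | 9/8.2 = 1.10 | 1.05 |
| 1.0 | 9/9.0 = 1.00 | 1.00 |

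With an assumed item effect d = 0.4 and 50 per group, power is 51.6% for one item. For the total it is 90.2%, 76.5%, 64.6% and 55.4% at r = 0.3, 0.5, 0.7 and 0.9.

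**When the assumption fails.** If only m of the nine items respond, the ratio to a responding item becomes (m/9) × √(9/(1 + 8r)). For m = 3 and r = 0.5 it is (3/9) × 1.34 = 0.45, so the total does worse than the affected items.

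**Against a domain instead of an item.** For the four-item daily-activities domain the ratio is √{[9/(1 + 8r)] / [4/(1 + 3r)]} = 1.12, 1.06 and 1.03 at r = 0.3, 0.5 and 0.7.

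**The case against.** Four points can be made for the plan.

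First, a reader might infer that HEIS is modelled by item and nothing else. The documents do not support that firmly. The Section 14.3.7.1 sentence has a domain clause, and HEIS has domains. This stands as an ambiguity, but it does not reach the total, and two of the four domains are single items.

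Second, a reader might infer that the total will never be tested. Section 14.3.12 says that the statistical analysis plan is finalised before the code is broken and may carry changes. The supplied text has no separate plan with more detail, so the supportable statement is that the text as supplied does not specify an analysis of the total.

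Third, the precision argument uses no trial data. It depends on equal item effects and an assumed correlation, and it compares the total with a single item, the least favourable comparator. That criticism stands. The sample-size multiples should not be read as a measured loss.

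Fourth, item-level results are a legitimate choice for an exploratory questionnaire. They parallel the symptom-level HESD analysis, and no decision rule depends on the number of contrasts; even the primary and secondary p-values are nominal (Section 14.3.4). This argues for keeping the item results, not for leaving the defined total without an analysis.

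**Conclusion.** The mismatch holds on the text and does not depend on any assumption: the endpoint is listed without an item qualifier, a total is defined, and the supplied analysis sections plan no estimate, interval or test for it. Followed as written, the plan gives nine nominal contrasts per dose, 36 at Week 16, perhaps with domain results, and no single HEIS estimate.

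The gain in precision is right in direction only when the effect is spread across items. Over assumed correlations of 0.3 to 0.9 with equal item effects, the ratio is about 1.63 to 1.05. It reaches 1 at full correlation and can fall below 1 if few items respond.

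The point is minor. HEIS is an other endpoint with no confirmatory claim, and the dose-response conclusion on IGA treatment success is unaffected.

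**What to change.** In Sections 14.3.7.1 and 14.3.7.2, name change from baseline in HEIS total score as the lead HEIS analysis, using the same repeated-measures model with the HEIS total at baseline as covariate. Keep the planned item results, and the domain scores, as supportive, and say explicitly whether domains are modelled. Because the model has treatment-by-visit terms, one fit supplies both Week 16 and the earlier visits.

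The cost is small but not nil:
- One extra model. It adds 4 Week 16 contrasts to the 36, so the gain is a stated lead result, not a shorter list.
- A scoring rule for a missing or inapplicable item. Section 11.7.1.2 has none, and one item concerns work, whereas the WLQ is limited to subjects with a paid job.

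Making the items purely descriptive is not needed, and it would discard estimates that the plan specifies twice. If item-level analysis was the real intent, adding the qualifier to the HEIS entries in Panel 3, as is done there for HESD, removes the inconsistency but still leaves no single HEIS estimate. Either change uses data already being collected and should be made before unblinding.
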